2 STUDY OBJECTIVES

2.1 Primary Objective

This is a prospective, nonrandomized, sequential data collection study to evaluate the ability of RPVi to predict fluid responsiveness in comparison with other dynamic parameters including SVV and/or PPV. Although this is a non-interventional study, focused on data collection, patients will be assigned to one of the two study groups with different tidal volumes: 6 ml/kg IBW and 8 ml/kg IBW. The research data will not be used to modify the subject's standard of care.

Specific aims:

- Evaluate the clinical utility of the RPVi as a predictor of fluid responsiveness in mechanically ventilated patients at two specific tidal volumes (6 ml/kg IBW and 8 ml/kg IBW).
- Characterize the correlations between the RPVi and PPV and/or SVV, as measured by FDA cleared comparator systems, as predictors of fluid responsiveness at two specific tidal volumes (6 ml/kg IBW and 8 ml/kg IBW).

Hypothesis (constructed as the null):

- RPVi as a dynamic monitor of cardiac function will not predict a subsequent increase in cardiac output following the administration of a fluid bolus of a crystalloid solution at a tidal volume of either 6 or 8 ml/kg IBW in intubated, mechanically ventilated patients.

- Changes in RPVi will not differ from concurrent changes in PPV and/or SVV, as measured by FDA cleared comparator systems following the administration of a fluid bolus of a crystalloid solution at a tidal volume of either 6 or 8 ml/kg IBW in intubated, mechanically ventilated patients.

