8 STATISTICAL PLAN

Prior studies of the predictive abilities of dynamic monitors of cardiac function with respect to cardiac output have established that sample sizes of 50 patients are sufficient to characterize the performance of the monitor. However, based on an ongoing Masimo study at another clinical test site, preliminary data received suggests that, of the first 83 subjects enrolled approximately 29% were responders. Therefore, in order to analyze the ability of RPVi, the sample size will be increased to a total of up to 150 patients. The first group of up to 100 subjects will be used to gather data to determine the thresholds for fluid responsiveness that would be used for the second group of 50 subjects. The second group will be the validation set to be used to evaluate study objectives in **section 2.1**. As such, the study will be registered on ClinicalTrials.gov but only results from the validation phase will be posted.

Normality of distribution will be tested before any statistical evaluation by using the Kolmogorov- Smirnov method. Descriptive statistical data will be reported as mean \pm SD. Except for the bias between both methods (RPVi vs PPV/SVV and SV/CO measurements). Comparisons between PPV/SVV and RPVi and between CO/SV measurements will be performed with a paired student t test. PPV/SVV and RPVi as well as SV/CO measurements will be compared using Bland and Altman. In order to evaluate the ability of RPVi to reliably detect changes in PPV/SVV and for CO measurements to accurately track Flotrac CO changes we will use a method based on polar plotting of PPV/SVV and RPVi and CO measurements changes over consecutive cycles as described by Critchley et al. We will exclude from this analysis small changes of mean value of

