PPV/SVV and RPVi and CO measurements less than 3%. In this method, a good trending ability requires an angular bias no greater than ± 5 degrees and a SD for the polar angle of less than ± 15 degrees. In this method, simultaneous changes of each indices of consecutive validated respiratory cycle will be reported on a polar plot. The polar angle will be derived from the ratio of the changes of the two indices such a ratio close to one led to a null angle with the x axis, this angle approach a 90 degrees angle when the ratio diverges from one. The radius will be the mean of the simultaneous changes of the two indices between two consecutive validated respiratory cycles. In these conditions a mean angle and its SD can be calculated.

The strength of linear dependence between PPV/SVV and RPVi and SV/CO measurements for all patients will be measured by the Pearson coefficient of correlation. The mean of correlation coefficients and comparison between correlation coefficients will be performed after a Fischer's transformation. In order to analyze the ability of RPVi to correctly classify the respiratory cycle as responder or non-responder after a volume loading in respect to a theoretical threshold value of PPV/SVV of 12%, we will measure the area under the curve of a Receiver Operating Characteristic (ROC) curve. Then the selected value of RPVi for each patient will be the one which maximized the Youden index (sensitivity + (specificity - 1)). The agreement between the two classifications will be quantified by the Kappa score for each patient, taking as threshold value of RPVi the individual value determined by the ROC curve. The reported mean values of areas under ROC curves and Kappa scores will be therefore calculated from the individual values. Taking the intra patients coefficient of correlation as a dependent variable, we will estimate its relationship with potentially explanatory variables by using univariate analysis, including Student t test for qualitative data and correlation for quantitative data and multivariate analysis by multiple linear regression. Categorical binary variable will be transformed into dummy variables. Other correlations will be evaluated by Pearson coefficient.

For all comparisons, a P value < 0.05 will be considered significant. Statistical analysis will be performed using SPSS software version 13.0 for Windows (SPSS Inc., Chicago, IL).

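### Section 8 specifies no analysis of pre-bolus RPVi against the change in stroke volume or cardiac output that hypothesis 1 is about

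*Combined protocol and SAP*

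**What the plan says.** Section 2.1 states hypothesis 1 as a null: "RPVi as a dynamic monitor of cardiac function will not predict a subsequent increase in cardiac output following the administration of a fluid bolus", at a tidal volume of 6 or 8 ml/kg IBW. Section 7 has SV and/or CO measured before the volume expansion and again after it, in patients for whom the bolus is not contraindicated.

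Section 8 then lists the analyses:

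- Paired t tests, Bland-Altman and polar plots set RPVi against PPV/SVV, and SV/CO measurements against each other.
- A correlation: "The strength of linear dependence between PPV/SVV and RPVi and SV/CO measurements for all patients will be measured by the Pearson coefficient of correlation".
- Coefficients are averaged, and a "comparison between correlation coefficients will be performed after a" Fisher transformation. No test is named.
- ROC, Youden index and Kappa classify respiratory cycles, with a PPV/SVV value of 12% as reference.
- A closing line leaves other, unnamed correlations to Pearson's coefficient.

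On size, section 8 asserts that "sample sizes of 50 patients are sufficient to characterize the performance of the monitor". It then reports from another study that "of the first 83 subjects enrolled approximately 29% were responders", and says that "the sample size will be increased to a total of up to 150 patients". Up to 100 patients set the thresholds "that would be used for the second group of 50 subjects"; the second group is the one used for the objectives.

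**The concern.** The target of hypothesis 1 is a change within a patient after the bolus. The analyses named in section 8 either compare RPVi with another dynamic index or, on one reading of the correlation sentence, relate it to SV/CO values without mentioning change. Agreement with PPV/SVV is not prediction of a rise in cardiac output, and the level of SV or CO is not the response to fluid. The data for a direct test are collected, but the plan does not say how they will be used.

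Two things are at stake. First, the choices that decide the answer (SV or CO, absolute or percent change, continuous or yes/no, pooled or per tidal volume) stay open until the data are seen. Second, if the gap is filled only by pointing the ROC at a yes/no SV/CO response, the validation set would hold about 14 or 15 responders. The low responder share is the plan's own reason for enlarging the study, yet the set that answers the objectives has 50 patients.

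**Working it through.** **1. The plan's own figures.** 24/83 = 28.9%, which agrees with the stated 29%. 100 + 50 = 150. Expected responders in the validation set: 0.29 × 50 = 14.5. The 50 itself cannot be re-derived, because section 8 gives no power, effect size or formula.

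**2. Hypothesis against analyses.** Hypothesis 1 needs pre-bolus RPVi on one side and the SV/CO change on the other. No analysis named in section 8 has that pair. The t test, Bland-Altman and polar plots pair RPVi with PPV/SVV and CO with CO. The ROC family pairs RPVi with PPV/SVV of 12%. The correlation sentence either keeps the two families apart or relates RPVi to SV/CO measurements. Elsewhere section 8 does refer to changes when it means them, as in the polar plots.

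**3. What the continuous change would add over a yes/no SV/CO label.** Assumptions, none from the documents except the 29%: bivariate normal relation, responders are the top 29%, two-sided test at the stated 0.05 (sidedness is not given).

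- Relative efficiency of the label = φ(z)² / [p(1 − p)]. With p = 0.29, z = 0.553 and φ = 0.3423: 0.1172 / 0.2059 = 0.569.
- Equivalent multiplier: 1/0.569 = 1.76 for a t-type comparison. For a rank (AUC) test, multiply by π/3: 1.84.
- Sensitivity to the responder share (t-type / AUC): 20%, 2.04 / 2.14; 40%, 1.61 / 1.68.
- Fisher-z power = Φ[atanh(r)·√(n − 3) − 1.96]. For r = 0.4, n = 50: 0.4236 × 6.856 − 1.96 = 0.944, power 83%. With the label, r falls to 0.4 × √0.569 = 0.302, giving 0.3114 × 6.856 − 1.96 = 0.175, power 57%.

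Simulation with an AUC test for the label:

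| True r | n | Continuous | Label |
|---|---|---|---|
| 0.3 | 50 | 57% | 34% |
| 0.4 | 50 | 84% | 55% |
| 0.5 | 50 | 97% | 77% |
| 0.4 | 25 (assumed per tidal volume) | 53% | 29% |

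**4. Where the gain fails** (n = 50, 29% responders, simulated). With a heavy-tailed response (t, 3 df, r = 0.40) the powers are 86% against 79%. If RPVi is shifted by 0.8 SD between responders and non-responders but is unrelated to the size of change within each class, they are 44% against 67%: the label wins.

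**5. Comparing RPVi with PPV/SVV as predictors.** If their between-patient correlations with the SV/CO change are compared, the two coefficients come from the same patients and share a variable. Take 0.60 against 0.40 at n = 50: difference in Fisher z = 0.6931 − 0.4236 = 0.2695. An independent-sample test uses SE = √(2/47) = 0.206, so z = 1.31 whatever the overlap. A Meng-type test uses z = 0.2695·√{47 / [2(1 − r_x)h]}, where r_x is the correlation between the indices, h = (1 − 0.26f)/0.74 and f = (1 − r_x)/1.48. This gives z = 2.56, 1.66 and 1.43 at r_x = 0.8, 0.5 and 0.3.

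| Index correlation | Independent Fisher z, simulated power | Meng-type, simulated power |
|---|---|---|
| 0.8 | 10% | 76% |
| 0.5 | 20% | 39% |
| 0.3 | 24% | 30% |

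**The case against.** The strongest reply is that the power comparison has no counterpart in the plan. A reader might infer that the plan's responder analysis has 55% power, or that the plan wastes nearly half its patients. The documents do not support that: section 8 contains no SV/CO responder analysis, so 84% against 55% compares two ways of filling the gap. This stands.

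A reader might also infer that RPVi is never related to SV/CO at all. That is too firm. The correlation sentence can be read as including RPVi with SV/CO measurements, and the closing line on other correlations could cover almost anything. Neither specifies the change, however. Nor is the change available in every patient, since the bolus is withheld when contraindicated.

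It is also fair that a validation set for a fixed threshold naturally yields sensitivity and specificity, and that a threshold-type relation favours classification, as step 4 shows. This is a reason to keep classification, not to leave the change unanalysed.

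Finally, one might infer that the planned Fisher comparison is wrong. Section 8 names no independent-sample test, and its references to mean coefficients and to coefficients within patients suggest that it may mean correlations across cycles, where the overlap problem need not arise. The point on dependent correlations is therefore conditional.

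**Conclusion.** The gap is real: section 8 prespecifies no analysis of pre-bolus RPVi against the post-bolus change in SV or CO, so hypothesis 1 has no explicit test. This rests on the text of sections 2.1, 7 and 8 and on no numerical assumption. Section 3 was not in the text reviewed; if it defines a response on SV or CO, section 8 still has to say how RPVi is tested against it.

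The size of the benefit from using the continuous change is conditional. It is about 1.8 times as many patients relative to a yes/no SV/CO label, given bivariate normality and a 29% responder share borrowed from another study. Because the hypothesis is stated at two tidal volumes, the pooled power overstates what each group can show. The loss from an independent-sample comparison of correlations runs from small to large with the correlation between the indices, and arises only if that test is used between patients.

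This should be changed before the validation data are analysed.

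**What to change.** In section 8, for the validation set:

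- Regress the percent change in SV (or CO; name which) from before to after the bolus on pre-bolus RPVi, one record per patient. Include assigned tidal volume and its interaction with RPVi, or give estimates per tidal volume. Add a rank-based sensitivity analysis.
- Do the same for PPV and SVV.
- Report alongside it the sensitivity, specificity and ROC of RPVi against a response defined on SV/CO, at the threshold fixed in the first group.
- If RPVi and PPV/SVV are compared through their between-patient correlations with the SV/CO change, use a method for dependent overlapping correlations (Meng-type or a bootstrap of patients).
- State that patients without a bolus, or without both measurements, do not contribute to these analyses, and report how many there are.

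The cost is SAP wording and a few models, with no new data or procedures. The drawback is that the regression assumes a roughly linear or monotone relation and loses power to the label if the relation is purely a threshold one, so both analyses are needed.

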The evolution of the pulse oximetry sensors to incorporate multi-wavelength technologies provided the opportunity to modify the PVi algorithm and improve clinical performance. As a dynamic monitor of cardiac function, PVi/ RPVi is analogous to pulse pressure variation (PPV), which may be derived through minimally-invasive means using beat-to-beat arterial pressure expressed as a percentage by the Philips IntelliVue (Philips Labs, Noord Brabant, NL) or stroke volume variation (SVV), which may be derived through minimally-invasive means using pulse contour analysis of the arterial pressure waveform as done by the Vigileo/Flotrac System (Edwards Labs, Irvine, CA) or Philips IntelliVue (Philips Labs, Noord Brabant, NL). Multiple studies have demonstrated that PPV and/or SVV is a valuable tool in predicting fluid responsiveness in mechanically ventilated patients.

The aim of this study is to test the ability of RPVi to predict fluid responsiveness in mechanically ventilated patients in the operating room and to compare it to other dynamic monitors of cardiac function in this setting.

This study will include patients [REDACTED] undergoing cardiac surgical procedures in which pulmonary and peripheral arterial catheters are standard monitors used for continuous monitoring of cardiac function and blood pressure, respectively. Patients with cardiac arrhythmias and intracardiac shunts will be excluded. Patients will be assigned to one of the two study groups with different tidal volumes: 6 ml/kg IBW and 8 ml/kg IBW. Both tidal volumes are within the range that is commonly used intra-operatively. In patients without significant pulmonary disease there is no significant risk or benefit associated with either tidal volume, however, there is evidence of decreased utility of the dynamic monitors of cardiac function (PPV/SVV) at lower tidal volumes. Attention to the tidal volume will aid the assessment of the utility of RPVi as a monitor of cardiac response to fluid administration.

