4 SUBJECT SELECTION AND WITHDRAWAL

4.1 Number of Subjects

There will be up to 150 subjects enrolled into this study, divided into two groups. There will be no protocol or procedural differences between the groups. The first group of up to 100 subjects will be used to gather data to determine the thresholds for fluid responsiveness that would be used for the second group of 50 subjects. The second group will be the validation set to be used to evaluate study objectives. The anticipated duration of subject participation in this study will not exceed 1 visit. The study enrollment period is expected to be approximately 2 years.

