7 STUDY PROCEDURES

- Patients are assigned to be ventilated in a volume controlled mode with a tidal volume of either 6 or 8 $\text{ml} \cdot \text{kg}^{-1}$ of ideal body weight (Devine formula) at a frequency [REDACTED]. Positive end-expiratory pressure is to be set [REDACTED] according to the attending physician.
- Anesthesia is induced as per standard of care. Radial and pulmonary arterial catheters inserted as per standard of care.
- All required sensors are placed as per the corresponding instructions for use for the various measurements
- All patients are to be studied [REDACTED] with no changes in anaesthetic protocol and no volume expansion. Unless clinically contraindicated, patients will receive an intravenous volume expansion consisting of [REDACTED] given over [REDACTED].
- Baseline set of haemodynamic measurements (stroke volume and or cardiac output) are to be performed prior to the intravenous volume expansion.
- A repeat set of hemodynamic measurements are to be performed [REDACTED] after volume expansion.

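### The only ROC analysis in section 8 uses PPV/SVV of 12% as its reference, so it measures agreement with PPV/SVV and does not test whether RPVi predicts the cardiac output response

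*Combined protocol and SAP*

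**What the plan says.** - **Section 2.1.** The first specific aim is "Evaluate the clinical utility of the RPVi as a predictor of fluid responsiveness in mechanically ventilated patients at two specific tidal volumes" (6 and 8 ml/kg IBW). The first null hypothesis is that RPVi "will not predict a subsequent increase in cardiac output following the administration of a fluid bolus of a crystalloid solution", at either tidal volume. The second null hypothesis compares changes in RPVi with concurrent changes in PPV and/or SVV.
- **Section 7.** "Baseline set of haemodynamic measurements (stroke volume and or cardiac output) are to be performed prior to the intravenous volume expansion". A repeat set follows the expansion. Volumes and timings are redacted.
- **Section 8, ROC paragraph.** RPVi is to classify the respiratory cycle "as responder or non-responder after a volume loading in respect to a theoretical threshold value of PPV/SVV of 12" per cent. A Youden-optimal RPVi value is chosen for each patient, kappa is computed for each patient at that individual value, and the reported AUCs and kappas are means of the individual results.
- **Sections 4.1 and 8.** The first group of up to 100 subjects serves to "determine the thresholds for fluid responsiveness that would be used for the second group of 50 subjects". Those 50 then form a validation set, on which the section 2.1 objectives are judged. Only validation results will be posted.
- **Section 8, on another sponsor study.** "of the first 83 subjects enrolled approximately 29% were responders".
- **Section 1.1.** The protocol accepts that "there is evidence of decreased utility of the dynamic monitors of cardiac function (PPV/SVV) at lower tidal volumes".

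**The concern.** An ROC analysis answers the question set by its reference standard. Here the reference is another index, PPV or SVV, cut at 12%. Null hypothesis 1 concerns what cardiac output does after the bolus. PPV/SVV labels may correlate with that response, but they do not measure it.

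Three consequences follow:

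- A high AUC could be reported as prediction of fluid responsiveness when it shows only that RPVi tracks PPV/SVV.
- By the protocol's own account the reference may be weakest at 6 ml/kg, one of the two settings named in the hypothesis. If RPVi predicted better than PPV/SVV, it would be marked down for disagreeing with them.
- The two-stage design needs one RPVi threshold from the first group to test in the second. The only derivation in section 8 yields a separate cut-off per patient, with no stated rule for turning these into one value.

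**Working it through.** **1. Which section 8 analysis addresses null hypothesis 1?**

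| Analysis in section 8 | What is compared | Uses post-bolus CO/SV change as the outcome? |
|---|---|---|
| Paired t test, Bland-Altman | RPVi with PPV/SVV; CO/SV measurements with each other | No |
| Polar plot | Changes in RPVi with changes in PPV/SVV; CO changes with Flotrac CO changes | No |
| Pearson correlation | PPV/SVV, RPVi and SV/CO, pairing unclear | Not stated: no pre-bolus predictor or post-bolus change is named |
| ROC, Youden, kappa | RPVi with PPV/SVV at 12%, by cycle within patient | No |
| Multiple regression | Intra-patient correlation coefficient on explanatory variables | No |

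**2. Could the ROC sentence be loose wording for a CO-response reference?** No. Section 7 as supplied describes one volume expansion with one baseline and one repeat measurement, so each patient has one CO change. A within-patient ROC against that change would contain a single outcome class and could not be computed. The per-patient procedure works only with a reference that varies from cycle to cycle, such as PPV/SVV.

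**3. The plan's own figures.** 24/83 = 28.9%, which agrees with the stated 29%. The validation size of 50 comes with no formula, power or precision target, so there is nothing to reproduce.

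**4. Does agreement with PPV determine prediction of CO?** Illustration with trivariate normal RPVi, PPV and CO change, 400,000 draws per scenario. Assumptions: corr(PPV, CO change) = 0.4, and both references cut at the 71st percentile (29% positive). No correlation comes from the documents.

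| corr(RPVi, PPV) | AUC against PPV cut | AUC against CO response at corr(RPVi, CO change) = 0 / 0.2 / 0.4 / 0.6 / 0.7 |
|---|---|---|
| 0.5 | 0.74 | 0.50 / 0.59 / 0.69 / 0.79 / 0.84 |
| 0.7 | 0.84 | 0.50 / 0.59 / 0.69 / 0.79 / 0.84 |
| 0.9 | 0.94 | same values, but see below |

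At corr(RPVi, PPV) = 0.9 the admissible range of corr(RPVi, CO change) is 0.9 × 0.4 ± √[(1 − 0.81)(1 − 0.16)] = 0.36 ± 0.40, or −0.04 to 0.76. The values 0 and 0.7 lie near those limits, so the 0.5 and 0.7 rows are the fair illustration.

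A second model lets RPVi relate to CO only through PPV, with 40% of cycles above the PPV cut. If PPV does not predict CO, null hypothesis 1 is true and the AUC against CO response is 0.50. The AUC against the PPV cut is still 0.83 to 0.94 for RPVi-PPV correlations of 0.7 to 0.9.

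**5. Within-patient feasibility.** A patient contributes an AUC only if some cycles lie on each side of 12%. Assume 100 cycles per patient, mean PPV 8 to 10%, between-patient SD 4 and within-patient SD 1.5 to 3. Then about 22 to 45 of 50 patients qualify, and the other 5 to 28 have no AUC or cut-off.

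**6. Locked or re-optimised threshold.** In 4,000 simulated studies of 100 + 50 subjects (29% responders, assumed corr(RPVi, CO change) = 0.6), a pooled Youden threshold has a mean index of 0.50 in the first group and 0.40 when locked and applied to the 50. Re-optimising in the 50 would show 0.53.

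**7. Precision with the right reference.** 50 × 0.29 = 14.5 responders (binomial 95% range 8 to 21). The Hanley-McNeil formula for AUC *A* is

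SE² = [A(1−A) + (n₁−1)(B₁−A²) + (n₀−1)(B₂−A²)]/(n₁n₀), with B₁ = A/(2−A) and B₂ = 2A²/(1+A).

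- A = 0.75, 14 v 36: B₁ = 0.600, B₂ = 0.643. SE² = (0.1875 + 0.4875 + 2.8125)/504 = 0.00692, so SE = 0.083 and the 95% CI is 0.59 to 0.91.
- A = 0.70, 7 v 18 (assumed even split by tidal volume): SE = 0.125, CI 0.45 to 0.95.
- Exact CIs: sensitivity 11/14 = 0.79 (0.49 to 0.95); specificity 28/36 = 0.78 (0.61 to 0.90).
- Paired comparison of AUCs 0.84 and 0.69 in 50 subjects (DeLong, 4,000 simulated sets): half-width 0.135 and power 0.59 at corr(RPVi, PPV) = 0.7; half-width 0.181 and power 0.39 at 0.4.

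**The case against.** The sponsor evidently has a patient-level responder in mind. Section 8 cites a responder rate and fluid-responsiveness thresholds, and section 7 measures SV and/or CO around the bolus. The text between sections 2.1 and 4 was not available and section 7 is partly redacted, so an endpoint or responder definition may exist there. The Pearson sentence may also include RPVi against SV/CO. This limits how firmly one can say that the hypothesis goes untested in the whole plan. It does not alter the finding about section 8, whose ROC would still have the wrong reference for hypothesis 1.

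Section 8 also does not say which group its ROC applies to. It could be run in the first group and the individual cut-offs averaged for the second. That is possible, so the fair criticism is that no carry-over rule is stated, not that none could exist. The consequence for the validation set is conditional on applying the ROC paragraph there as written.

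Finally, every correlation and PPV distribution above is assumed. The feasibility and locking simulations are secondary to the choice of reference standard, and the conclusion does not rest on them.

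**Conclusion.** The concern holds, and the analysis is wrong as written for the first hypothesis. The ROC, Youden cut-offs and kappas in section 8 measure agreement with PPV/SVV at 12%, which belongs to the second aim. They do not test prediction of a cardiac output increase, and they do not compare RPVi with PPV/SVV as predictors of it. This follows from the text alone.

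The size depends on correlations the documents do not give. Under the assumptions shown, one AUC of 0.84 against PPV is compatible with anything from no prediction of CO response to an AUC of 0.84. This should be corrected before validation data are analysed.

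**What to change.** In section 8:

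1. Make the main analysis a patient-level ROC of pre-bolus RPVi against a responder flag in the validation set, with a 95% CI. Base the flag on the percentage rise in one named measure (CO or SV) from the pre-bolus to the post-bolus reading. Fix the percentage before validation data are seen, or cross-reference it if it is already defined elsewhere. Report the AUC overall and at 6 and 8 ml/kg IBW separately, the latter as estimation only.
2. Report the AUCs of pre-bolus PPV and/or SVV against the same flag, with the paired difference and its CI. This goes beyond hypothesis 1 but serves the comparative objective in section 2.1.
3. Derive one common RPVi threshold in the first group by a stated criterion, for example the Youden index on the pooled patient-level ROC. Lock it, and report sensitivity and specificity with exact CIs in the 50 validation subjects.
4. Keep the PPV/SVV 12% ROC and kappa as a secondary agreement analysis. State how many patients have cycles on both sides of 12%.

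**Cost.** No new procedure is needed. The sponsor must name CO or SV and confirm that it is recorded both before and after the bolus, because section 7 allows either or both. Reading times can be cross-referenced if they stand in the redacted text. Device and arterial waveform data are already transferred under section 10.5. The price is precision: intervals will be wide, most of all by tidal volume, and the paired comparison will have limited power.

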RPVi reflects measurements of ventilation induced respiratory changes in Pi over a period of time and is calculated as follows:

$$PVi \text{ or } RPVi = [(Pimax - Pimin)/Pimax] \times 100(%)$$

Multiple studies have demonstrated that PVi can predict fluid responsiveness in mechanically ventilated patients (Desebbe 2010) and can be used to optimize intraoperative fluid therapy (Desebbe 2008). Yin and Ho (2012) and Sandroni (2012) have provided meta-analyses confirming the clinical utility of PVi to guide clinical care. Among the available dynamic monitors of cardiac function in common clinical use (pulse pressure variation PPV, stroke volume variation SVV, corrected esophageal Doppler flow time FTc, etc.) the respiratory variations in the pulse oximeter plethysmographic waveform amplitude (pleth variability index PVi) has the advantage of being completely non-invasive.

The sensitivity of a dynamic monitor of cardiac function is dependent on the magnitude of the swings in the intrathoracic pressure associated with mechanical ventilation. During the introduction of these monitors into daily anesthetic management there has been a concurrent evolution in our intra-operative ventilator management protocols. During the past decade of practice, commonly recommended intraoperative tidal volumes have declined from 10 ml/kg to 8 ml/kg and now down to 6 ml/kg. Recommendations for the use of dynamic monitors as a guide for intraoperative fluid management stress that positive studies were done with controlled tidal volumes of 8 ml/kg and their sensitivity has not been established under conditions

including smaller tidal volumes. There is a pressing need to re-evaluate the performance and utility of these monitors under currently recommended respiratory management practices.

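### RPVi's ROC, cut-off and kappa rest on one underived 12% PPV/SVV label at both tidal volumes, so a 6-versus-8 ml/kg difference could be an artefact of the label

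*Combined protocol and SAP*

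**What the plan says.** - **Two tidal volumes.** Section 1.1: "Patients will be assigned to one of the two study groups with different tidal volumes: 6 ml/kg IBW and 8 ml/kg IBW". Section 2.1 asks for RPVi's performance at each volume, and its first hypothesis concerns a rise in cardiac output after a fluid bolus.
- **Doubt about the comparators at low volume.** Section 1.1 notes that "there is evidence of decreased utility of the dynamic monitors of cardiac function (PPV/SVV) at lower tidal volumes". It also says that "positive studies were done with controlled tidal volumes of 8 ml/kg and their sensitivity has not been established under conditions" with smaller volumes.
- **The reference label.** Section 8 introduces the ROC analysis with "In order to analyze the ability of RPVi to correctly classify the respiratory cycle as responder or non-responder after a volume loading", judged "in respect to a theoretical threshold value of PPV/SVV of 12" per cent. No derivation is given, and there is no separate value for PPV, for SVV or for either tidal volume.
- **RPVi's own cut-off.** This is fitted: "the selected value of RPVi for each patient will be the one which maximized the Youden index".
- **Agreement.** "The agreement between the two classifications will be quantified by the Kappa score for each patient", and the reported AUCs and kappas are means of the individual values.
- **Thresholds from the first group.** Section 4.1: "The first group of up to 100 subjects will be used to gather data to determine the thresholds for fluid responsiveness", for use in the next 50. Neither section 4.1 nor section 8 says which index or tidal volume is meant, or how these thresholds relate to the fixed 12%.

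**The concern.** Tidal volume is the factor that separates the study groups, and section 1.1 argues that it changes how dynamic indices behave. Yet the responder label in section 8 does not depend on it. If PPV/SVV readings are smaller at 6 ml/kg, fewer cycles pass 12% there, and those that pass are a different selection from those that pass at 8 ml/kg. RPVi's AUC, Youden cut-off and kappa are all computed against that label. They could then differ between volumes with no change in how well RPVi predicts the cardiac output response.

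At stake is the comparison the study was set up to make. A reader who sees a better or worse AUC at 6 ml/kg could not tell whether RPVi or the yardstick had changed.

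**Working it through.** **What can be reproduced.** The 12% has no inputs in the documents, so it cannot be re-derived. The other figures check: 100 + 50 = 150 subjects, and 24/83 = 28.9%, matching the 29% responder rate that section 8 takes from another site.

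**Illustration 1: what 12% would mean at 6 ml/kg.** Everything here except the 12% and the 29% is an assumption. PPV/SVV at 8 ml/kg is taken as normal, with mean 15 in true responders, 9 in non-responders and SD 4. At 6 ml/kg all values are multiplied by f: 1 (no change), 0.9 (a 10% fall) or 6/8 = 0.75 (proportional scaling).

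- Sensitivity = 1 − Φ((12 − 15f)/(4f))
- Specificity = Φ((12 − 9f)/(4f))
- Share labelled responder = 0.29 × sensitivity + 0.71 × (1 − specificity)

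| f | Sensitivity | Specificity | Labelled responder |
|---|---|---|---|
| 1 | 1 − Φ(−0.75) = 0.77 | Φ(0.75) = 0.77 | 39% |
| 0.9 | 1 − Φ(−0.417) = 0.66 | Φ(1.083) = 0.86 | 29% |
| 0.75 | 1 − Φ(0.25) = 0.40 | Φ(1.75) = 0.96 | 14% |

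With means from 14/10 to 16/8, sensitivity at f = 0.75 runs from 0.31 to 0.50 and specificity from 0.93 to 0.98. A cut-off scaled with the index (9% at f = 0.75) returns 0.77/0.77, but only because the model shrinks the SD too. With the SD held at 4, means of 11.25 and 6.75 and a 9% cut-off give Φ(2.25/4) = 0.71 for both.

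**Illustration 2: what section 8 would report.** The planned output is RPVi's AUC against the 12% label. RPVi was given the same assumed means and SD as PPV, with a residual correlation of 0.3 or 0.6 between the two (400,000 simulated draws). Both indices were scaled by f.

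| f | AUC against 12% label, correlation 0.3 | Same, correlation 0.6 | AUC against true response |
|---|---|---|---|
| 1 | 0.760 | 0.857 | 0.856 |
| 0.9 | 0.775 | 0.868 | 0.856 |
| 0.75 | 0.805 | 0.893 | 0.856 |

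Rescaling RPVi leaves its AUC unchanged, so all the movement comes from the label. RPVi predicts true response equally well in every row. PPV scored against its own label has AUC 1.000 throughout.

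**Missing values.** Section 8 averages AUCs computed within patients. A patient whose cycles all lie on one side of 12% has no ROC curve. If the index shrinks, patients wholly below 12% would be more common at 6 ml/kg. The plan does not say how they are handled.

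**The case against.** A reader might infer that the fixed 12% handicaps PPV/SVV against an RPVi with a tuned threshold. The plan does not support that. In section 8 the 12% is the reference label, and no analysis scores PPV/SVV at 12% against the cardiac output response, so PPV/SVV cannot lose. A handicap would arise only in a head-to-head against CO/SV change, which section 8 does not specify. The asymmetry is real, but its effect is to flatter agreement, because RPVi's threshold is fitted to the label.

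Nor do the documents show that 12% is wrong at 6 ml/kg. Decreased utility may mean poorer discrimination, which no new cut-off would cure. Section 1.1 states the mechanism for dynamic monitors in general, so RPVi may shrink too. The claim that most responders would fall below 12% holds in the steep scenario (40% above) and fails with a 10% fall (66% above).

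The effect on the planned output is also modest in the illustration, at about 0.04 in AUC. The paired t test, Bland-Altman, polar-plot and Pearson analyses do not use 12% at all. Finally, section 4.1 leaves room for thresholds by index and volume: they are unspecified, not excluded.

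All of this stands. It limits the point to the ROC, Youden and kappa step and leaves its size open. It does not explain why that step uses one unqualified PPV/SVV figure when section 2.1 names cardiac output as the outcome.

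**Conclusion.** The point holds for the ROC, Youden and kappa analyses. They depend on a label that, by section 1.1's own account, has least support at 6 ml/kg, and that differs from the outcome in section 2.1. A 6-versus-8 difference in RPVi's AUC or kappa could therefore be an artefact of the label.

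The documents do not fix its size. In the illustrations, the label's sensitivity for true response ranges from 77% down to 40%. RPVi's reported AUC moves from 0.760 to 0.805, or from 0.857 to 0.893, while its true AUC stays at 0.856. These figures rest on assumed means, SD, scaling and correlation. They show that the mechanism works and do not predict the result.

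The deeper cause is that PPV/SVV replaces the measured response as the reference. Recalibrating 12% by tidal volume would not cure that on its own. The plan should change here, because following it as written leaves the volume comparison uninterpretable in this step.

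**What to change.** In section 8:

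1. Make the main ROC analysis one observation per bolus, with responders defined by a prespecified change in CO or SV. Section 8 names no such change. If one is stated elsewhere in the protocol, refer to it.
2. Report the AUC of RPVi and of each recorded comparator (PPV and/or SVV) against that outcome, separately at 6 and 8 ml/kg, with confidence intervals.
3. In the first group, derive one group-level cut-off per index by the same rule for all indices, by tidal volume where responder numbers allow. Freeze these and apply them in the 50 validation subjects. The per-patient, per-cycle Youden rule cannot be reused, because each bolus gives a single response.
4. Keep the 12% agreement and kappa as a secondary analysis, shown by tidal volume, and say how patients without a computable ROC are handled.

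**Cost.** Section 7 already plans haemodynamic measurements before and after the bolus, so the change is mainly text and analysis. The price is precision. Assuming equal allocation (no ratio is stated), 100 first-group subjects and 29% responders, there are 50 × 0.29 = 14.5 responders per volume in the first group and 25 × 0.29 = 7.25 in validation. At a true sensitivity of 0.80, the rough 95% half-width is 1.96 × √(0.8 × 0.2/14.5) = 0.21 in the first group and 1.96 × √(0.8 × 0.2/7.25) = 0.29 in validation. Cut-offs by volume would be imprecise, and the report should say so. Because the protocol allows PPV and/or SVV, one of the two may be missing in some patients.
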